6.2 Benefits

The FARAPULSE Cardiac Ablation System is a Pulsed Electric Field (PEF) ablation system that produces contiguous transmural cardiac lesions to treat atrial fibrillation using an ablation procedure that is similar to other commercially available ablation catheters. More specifically:

- The device system is used during concomitant heart surgery like other commercially approved catheter systems.
- The device system is composed of similar biocompatible materials
- The device system is a non-thermal ablation technology with targeted tissue specific mechanism of ablation
- The device uses the standard open heart surgery technique.
- The device utilizes a standard irreversible electroporation generator to deliver energy in the form of ablation dose.

A fundamental difference between the FARAPULSE Cardiac Ablation System and other commercially released ablation systems used during concomitant heart surgery is that the pulsed electric field or irreversible electroporation energy is delivered through epicardial electrodes embedded in the catheter that surrounds the pulmonary veins.

As such, the potential risks are roughly equivalent to those associated with commercially released systems being used for cardiac ablation procedures during concomitant heart surgery. Currently, the complication rates for commercially available catheters are very low and have declined as physicians have continued to learn more about cardiac ablation techniques. Furthermore, FARAPULSE, Inc. has conducted bench and in-vivo testing to ensure safe use of the device during clinical investigation and ultimately compliance with Directive 93/42/EEC. Some tests results are pending and will be released before this feasibility study.

The epicardial ablation capabilities of the system provide several potential benefits compared to commercially released systems, including reduced procedure time, reduced fluoroscopy time, faster healing, better safety and improved long-term clinical outcomes.

In-vivo research has demonstrated that the system performs as expected and supports the risk estimations used and verified effective risk mitigation. All potential risks have been evaluated and mitigation strategies have been implemented to reduce potential risks to acceptable levels. The Sponsor has determined that the potential benefits of the system outweigh the potential risks and that the device is therefore safe for human use in the context of a clinical investigation.

There are no *guaranteed* benefits from participation in this study. It is also anticipated that once a physician learning curve is achieved, a reduced procedure and fluoroscopy time may be seen, since the energy delivery is done in 4 heart beats. Information gained from the conduct of this study may also be of benefit to other persons with the same medical condition.

7. Statistical Analysis and Endpoint Assessment

7.1 General Statistical Considerations

The primary objective of this study is to characterize the safety and feasibility of the FARAPULSE Cardiac Ablation System in subjects with paroxysmal atrial fibrillation undergoing cardiac surgery.

The study is a feasibility study with no formal hypothesis testing and therefore no required sample size. Study results will be presented using descriptive statistics. Results from this study will be used to design additional clinical studies.

All subjects will be followed on an intent-to-treat basis. The device performance will be assessed based on a per-protocol analysis of the primary safety and feasibility endpoints and secondary efficacy endpoints. An intent-to-treat analysis, along with other secondary analyses, will also be completed and reported.

Demographic, baseline clinical and disease characteristics, procedural results and primary, secondary and all additional endpoints will be summarized using descriptive statistics.

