5.8 Written Informed Consent

All subjects must provide written Informed Consent using the Ethics Committee approved Informed Consent Form before undergoing any study related procedures. Subjects cannot be asked to sign the Informed Consent document until the trial has been fully approved by the respective institution's EC and the Sponsor or their CRO representative has received and reviewed the specific EC-approved Informed Consent Form. Subjects who meet the general entry criteria will be asked to sign a Patient Informed Consent form as approved by the relevant regulatory authorities before any study-specific tests or procedures are performed. The Investigator or a designated member of his/ her staff should approach the subject to obtain written informed consent. As far as possible, non-technical language shall be used that is understandable to the subject. If the family of the subject is available, they should also be consulted. The background of the proposed study and the benefits and risks of the procedures and study should be explained. The subject should be provided with ample time to read the consent form and discuss it with their family and physician. The subject shall be informed that his/ her participation in the clinical investigation is confidential. The Informed Consent Form must be read and understood by the subject and the subject's questions answered. The form must be signed and dated by both the subject and investigator conducting informed consent before the subject undergoes any study related procedures. All subjects are to receive copies of their signed and dated Informed Consent Form. A copy of the approved informed consent form along with a copy of each patient's signed consent form will be maintained by each Investigator in a designated clinical study administrative file. The subject and the investigator must sign the consent form prior to enrollment. Subjects may not be consented after receiving any medication that might alter their ability to comprehend the consent form (e.g. sedatives, narcotics, etc.). Study personnel should explain that even if a subject agrees to participate in the study and signs the Patient Informed Consent form, the subject may not be eligible to participate if he/ she fails to meet the screening criteria.

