Written informed consent must be obtained prior to performing any protocol driven tests or any procedures that are not standard of care for a cardiac surgery that the subject is scheduled to undergo.

Once written consent has been obtained, the subject will be entered on a Screening Log, which will be maintained at each site. All subjects who provide written informed consent will be entered on the screening log regardless of whether or not they are enrolled in the study.

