5.9 Enrollment

Subjects that meet all the eligibility criteria and are deemed suitable by the investigator will be invited to participate in the study.

Subjects will be considered enrolled at the time of signing the informed consent.

Each subject will be assigned a unique study identification code to protect each subject's confidential health information. The unique study identity code will not include date of birth or subject's first and last initials and will be used to link study data and other study information to the subject in lieu of the subject name. The Subject Name Log will be used to link the unique study identity code to the subject and will be maintained at each site. This log will remain confidential and will not be provided to the Sponsor, but only used for reference when monitoring at the study site.

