7.6 Assessment of Feasibility

7.6.1 Primary Feasibility Endpoint

Proportion of subjects that achieve procedural success. Procedural success is defined as the creation of an electrically isolating "box" lesion encompassing the pulmonary veins and posterior left atrium using the study device. Specifically, the ability of the device to create a contiguous line of electrical block in the specified region of the left atrium.

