7.7 Assessment of Safety

7.7.1 Primary Safety Endpoint

A composite safety endpoint consisting of the proportion of subjects that experience one or more of the following serious adverse events (SAEs) related to the investigational procedure and/or device within 30 days of the PEF ablation procedure or hospital discharge, whichever is later, except as noted below:

- Cardiac death
- Stroke and/or transient ischemic attack (TIA)
- Myocardial infarction (MI)
- Excessive bleeding or
- Atrio-esophageal fistula
- Persistent post-surgical phrenic nerve paralysis at 12 months
- Severe pulmonary vein stenosis

All adverse events (AEs) will be adjudicated for seriousness as well as device and procedure relatedness.

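### Section 7.1 leads with an undefined per-protocol analysis for both primary endpoints, safety included, and the intent-to-treat report only partly makes up for it

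*Combined protocol and SAP*

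**What the plan says.** Section 7.1 makes three statements about analysis sets.

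- On follow-up: "All subjects will be followed on an intent-to-treat basis".
- On the main assessment: "The device performance will be assessed based on a per-protocol analysis of the primary safety and feasibility endpoints and secondary efficacy endpoints".
- On what else is reported: "An intent-to-treat analysis, along with other secondary analyses, will also be completed and reported". The word 'other' puts intent-to-treat among the secondary analyses, so per-protocol leads.

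Per-protocol is mentioned nowhere else. The document gives no membership rule, no list of disqualifying deviations, no decision-maker and no time by which the set is fixed. Sections 7.6 and 7.7 restate the endpoints as proportions of subjects without naming a denominator. Section 7.4 rules out imputation and uses available data only.

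Procedural success in 7.6.1 requires an isolating box lesion made with the study device: "Specifically, the ability of the device to create a contiguous line of electrical block in the specified region of the left atrium". The primary safety endpoint in 7.7.1 counts listed related events "within 30 days of the PEF ablation procedure or hospital discharge, whichever is later".

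On enrollment, 5.9 says: "Subjects will be considered enrolled at the time of signing the informed consent". Section 5.8 says: "All subjects who provide written informed consent will be entered on the screening log regardless of whether or not they are enrolled in the study". The cap of 25 is on subjects enrolled in 5.5 and on patients studied in 7.2.

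**The concern.** In a first-in-man device study, being unable to place the catheter or finish the ablation is itself a feasibility result. A complication that stops the procedure is a safety result. A per-protocol set without a written rule lets such subjects leave both denominators, and lets that be decided after their outcomes are known. Leaving them out can only raise the success proportion or leave it unchanged, while the safety proportion can move either way.

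The intent-to-treat figure would normally be the safeguard, but its population is not defined either. If it counts everyone who signed consent, never-treated subjects lower both proportions. No set of attempted or treated subjects is planned, so neither analysis is certain to show success and harm among those in whom the device was tried. Section 7.1 says the results will be used to design further studies, so these proportions are the trial's main product.

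**Working it through.** The plan has no power, performance goal or calculated sample size to reproduce. The check is a reading of the text followed by an illustration.

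**Reading.**
1. A subject with a failed placement, an aborted procedure or an incomplete lesion cannot meet the 7.6.1 definition. Each is a failure if counted; only inclusion is open.
2. An undefined per-protocol set guarantees inclusion of none of the three. Section 7.4 adds a second route: a subject with no post-ablation map could be treated as missing rather than failed.
3. Under 5.9 every subject who signs consent is enrolled. Under the screening-log sentence in 5.8 a subject may have consented and not be enrolled. Both cannot hold, so the intent-to-treat denominator could be all consented subjects or a later subset.

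**Inputs.** The documents give only the cap of 25. They give no rate of failed placement, aborted procedure or screen failure, so all counts below are assumed. Let *n* be the number attempted, *i* incomplete lesions (kept as failures here) and *a* failed or aborted cases left out. Intervals are Clopper-Pearson, two-sided 95%.

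**Feasibility.** Successes s = n − i − a; gap = s/(n − a) − s/n. With n = 20, i = 1, a = 2, s = 17:
- all attempted: 17/20 = 85.0% (62.1 to 96.8)
- the 2 left out: 17/18 = 94.4% (72.7 to 99.9), a gap of 9.4 points
- the incomplete lesion left out as well: 17/17 = 100%

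Gap in percentage points with i = 1:

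| a left out | n = 20 | n = 25 |
|---|---|---|
| 0 | 0 | 0 |
| 1 | 18/19 − 18/20 = 4.7 | 23/24 − 23/25 = 3.8 |
| 2 | 17/18 − 17/20 = 9.4 | 22/23 − 22/25 = 7.7 |
| 3 | 16/17 − 16/20 = 14.1 | 21/22 − 21/25 = 11.5 |

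**Safety.** Assume 2 subjects with events among 20 attempted: 2/20 = 10.0% (1.2 to 31.7). With the 2 failed or aborted cases left out:
- neither had an event: 2/18 = 11.1% (1.4 to 34.7)
- one did: 1/18 = 5.6% (0.1 to 27.3)
- both did: 0/18 = 0% (0 to 18.5)

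**Consent-based denominator.** Assume 25 consented and 20 attempted. Success is 17/25 = 68.0% (46.5 to 85.1) and events are 2/25 = 8.0% (1.0 to 26.0).

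**The case against.** The strongest reply is that little depends on this. The study is descriptive, with no hypothesis, performance goal or go/no-go threshold. Both analyses will be reported, so a difference between them would be visible. Adverse events are adjudicated (7.7.1, 10.12) and SAEs are tabulated by interval (7.7.2). The illustrative intervals overlap widely, and the 0% safety figure needs both events to fall in the two excluded subjects. All of this stands and limits the harm. It does not say who is in the leading analysis.

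Four stronger readings are tempting, and the documents do not support them.

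- *Failed placements have no defined outcome.* They do: 7.6.1 makes them failures once counted.
- *The intention-to-treat label in 5.1 contradicts 7.1.* The label can be read with the follow-up statement in 7.1, so no conflict is shown.
- *Section 5.8 as a whole contradicts 5.9.* Its requirement to sign before enrollment fits enrollment on signing, and its warning that after signing "the subject may not be eligible to participate if he/ she fails to meet the screening criteria" concerns eligibility. The direct clash is the screening-log sentence.
- *Many never-treated subjects will enter the intent-to-treat set.* Sections 5.9 and 10.2.3 put an eligibility judgement before consent, which may keep the number small. Some baseline imaging that bears on exclusions may follow consent, but 5.8 requires consent first only for protocol-driven or non-standard tests. The number cannot be predicted from the text.

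**Conclusion.** The point holds and should be fixed. The lead assessment of both primary endpoints uses a set with no definition, and the secondary intent-to-treat analysis repairs this only in part while 'enrolled' has two meanings. With 1 to 3 failed or aborted cases left out of 20 to 25 attempted, and one incomplete lesion kept as a failure, reported success would be 3.8 to 14.1 points too high; it is unaffected if none is left out. The safety proportion could rise slightly or fall to zero. These sizes rest wholly on assumed counts. Confidence is high that the membership rule is missing and lower on how far a consent-based denominator would dilute the results.

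A reader might infer that safety events would disappear from the record or that an error rate is inflated. Neither follows: SAEs are still adjudicated and tabulated, and nothing is tested. The risk is a misleading headline proportion.

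**What to change.** In 7.1:

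1. Report both primary endpoints mainly in all subjects in whom placement or use of the study catheter was attempted. Count failed placement and aborted or incomplete ablation as procedural failure, not as missing under 7.4.
2. Keep per-protocol as a supportive analysis. Fix its criteria before data review and make them independent of procedural outcome and adverse events.
3. Use one meaning of 'enrolled': reconcile the screening-log sentence in 5.8 with 5.9, and say in 5.5 and 7.2 whether the cap of 25 counts consented or treated subjects.
4. Define the intent-to-treat set from that meaning. List consented subjects with no attempted use separately, with reasons and any SAEs.

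The safety window in 7.7.1 need not change for this.

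The cost is mainly wording. Procedural details (5.13.2), device use and malfunctions (11.4) and exit forms (11.2.2) are already collected. However, 5.13.2 does not list placement attempts or reasons for stopping, so the CRF must record attempted placement if it does not already. The sponsor should also expect that reported success may be lower than the per-protocol figure.

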7.2 Sample Size Justification

The IMPACT Study is a first-in-man trial and as such a relatively small number of patients, up to 25, will be studied at up to three sites. The safety and feasibility of the device will be analyzed before embarking on larger fully powered clinical studies to analyze safety and efficacy of the FARAPULSE Cardiac Ablation System.

7.3 Demographic, Safety, Feasibility and Efficacy Data

Demographic and baseline clinical and disease characteristics will be summarized in tables. For continuous variables, the summary will include number, mean, and standard deviation and 95% confidence intervals. Summaries for categorical variables will include the number and percent of subjects in each category.

7.4 Imputation for Missing Data

Imputations for missing data in (e.g., withdrawn subjects, loss to follow-up, missing data) will not be performed. Analyses will be performed with all available data only.

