5.4.5 Additional Observations

Proportion of subjects that achieve therapeutic success. Therapeutic success is defined as freedom from AF, AFL (atrial flutter) and AT (atrial tachycardia, not including sinus tachycardia) following the blanking interval through Month 12. Proportion of subjects that achieve therapeutic success. Therapeutic success is defined as freedom from AF, AFL (atrial flutter) and AT (atrial tachycardia, not including sinus tachycardia) following the blanking interval through Month 12. For subjects to be considered a therapeutic success, they will have to be free of a confirmed AF, AFL or AT episode lasting 30 seconds or more after completion of the blanking interval. If a qualifying episode of AF, AFL or AT is found during the 24-hour continuous ECG monitor at Months 6 or 12, during any scheduled or unscheduled 12-lead ECG, or during the use of an event monitor after the blanking interval, the subject will be considered a therapeutic failure. In addition, subjects will be considered a therapeutic failure if they have a repeat ablation procedure at any time through Month 12 or if they received DC cardioversion or Vaughan-Williams Class I or III antiarrhythmic drug therapy for the treatment or prevention of AF, AFL or AT after the end of the blanking interval through Month 12. However, subjects will not be considered therapeutic failures if they received DC cardioversion or Vaughan-Williams Class I or III antiarrhythmic drug therapy for treatment of non-AF arrhythmias during the blanking period. Finally, any subject death after the blanking interval and prior to the Month 12 visit will be adjudicated by the CEC. In the absence of evidence regarding the presence or recurrence of AF following the blanking period, these subjects will be considered lost to follow-up. If, on the other hand, there has been evidence of the presence or

recurrence of AF following the blanking period, these subjects will be considered therapeutic failures.

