5.11 Lost to Follow-up

If the investigator has attempted to contact a subject at least three times within 60 days and received no response, the subject may be considered lost to follow-up. The investigator will document that a minimum of three attempts were made to contact the subject, including sending a certified letter if current address is known, prior to exiting the subject from the trial.

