5.13.3 Pre-Discharge

Prior to hospital discharge the following data will be collected:

- Use, changes in or discontinuation of anticoagulation, rate control and/or antiarrhythmic medications;
- Cardioversion(s) since surgery;
- For subjects on warfarin, assessment of INR therapeutic levels (maintain as clinically indicated);
- For subjects on dabigatran, perform a PTT and, if required, a thrombin time (Section 4.7.2.7 Anticoagulation Regimen);

- Cardiac rhythm as determined by a 12-lead ECG on day of hospital discharge;
- Heart failure status as assessed by NYHA classification on day of hospital discharge; and Adverse Events.

5.13.4 1 Month Follow-Up

Discharged subjects will return for an office visit 30 days (± 7 days) postablation treatment. Subjects that continue to be hospitalized 30 days postablation will have their 30-Day Follow-Up assessment performed at discharge. At a minimum, the following data will be collected at 30 Day Follow-Up visit:

- Use, changes in or discontinuation of anticoagulation, rate control and/or antiarrhythmic medications;
- Cardioversions since last visit;
- For subjects on anticoagulants, assessment of INR/PTT therapeutic levels (maintain as clinically indicated):
- Cardiac rhythm as determined by a 12-lead ECG at the time of the visit;
- Heart failure status as assessed by NYHA classification at the time of visit;
- Any hospital readmissions, including admission and discharge dates, since discharge from the original procedure; and

5.13.5 3 Month Follow-Up

Subjects will return for an office visit at the end of the blanking period (90 days \pm 14 days post-ablation treatment). During the blanking period, any recurrence of AF will be documented; however, recurrences of AF, AFL or AT during this time will not be considered therapeutic treatment failures. Subjects are not permitted to undergo repeat ablation during the blanking period. If a repeat ablation procedure is performed during this time, the subjects will be considered a therapeutic treatment failure and exited from the study.

At a minimum, the following data will be collected at the end of the blanking period follow-up visit:

- Use, changes in or discontinuation of anticoagulation, rate control and/or antiarrhythmic medications;
- Cardioversions since last visit;
- Any additional ablation procedures performed;
- For subjects on anticoagulants, assessment of INR/PTT therapeutic levels (maintain as clinically indicated);

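### The 12-month therapeutic success proportion has no defined denominator; on the natural reading it keeps early failures and drops subjects who leave AF-free

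*Combined protocol and SAP*

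**What the plan says.** Therapeutic success is an additional observation in section 5.4.5, neither a primary nor a secondary endpoint. It requires freedom from AF, AFL and AT "following the blanking interval through Month 12". One event is enough for failure: "If a qualifying episode of AF, AFL or AT is found during the 24-hour continuous ECG monitor at Months 6 or 12", or on any 12-lead ECG or event monitor after blanking, the subject has failed. Repeat ablation at any time, and cardioversion or a Class I or III drug for these arrhythmias after blanking, also count as failure.

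Two rules deal with subjects who do not reach Month 12:

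- Deaths after blanking (5.4.5). Without evidence of AF: "In the absence of evidence regarding the presence or recurrence of AF following the blanking period, these subjects will be considered lost to follow-up". With such evidence, "these subjects will be considered therapeutic failures".
- Repeat ablation during blanking (5.13.5): "the subjects will be considered a therapeutic treatment failure and exited from the study".

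Section 5.11 describes when a subject may be declared lost, after contact attempts made "at least three times within 60 days and received no response, the subject may be considered lost to follow-up", but not how that subject enters the success proportion. Section 7.4 adds "Imputations for missing data in (e.g., withdrawn subjects, loss to follow-up, missing data) will not be performed" and then "Analyses will be performed with all available data only". Section 7.1 plans descriptive statistics only. No time-to-event method is named, and no denominator is defined for this proportion.

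**The concern.** Failure can be known early, but success can be known only at the end. Take two subjects lost at month 8, one with AF at Month 6 and one without. The first is a failure on available data. The second has no Month 12 status and, on the natural reading of 7.4, falls out of the calculation. The death rule works the same way: two subjects who die in the same month are classified differently solely because of prior AF. Whether a subject enters the denominator therefore depends on the outcome, and this can shift the proportion even when loss has nothing to do with AF.

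Section 7.1 says that the results will feed the design of later studies, and section 7.2 expects larger, fully powered ones. A success rate shifted by the counting rule would carry into their planning values, and the AF-free follow-up of subjects who left would go unused.

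**Working it through.** The plan gives no expected success rate, dropout rate or precision for this endpoint, so there is no figure to reproduce.

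**Inputs from the documents.** Up to 25 subjects (7.2). Visit windows of 180±30 and 365±30 days (Table 4). Event monitors between visits only for symptomatic subjects (5.13.5, 5.13.6.1).

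**Assumptions.** True 12-month success S = 70%, with 55% to 77% as a range. That range is the background figure for catheter ablation in 3.1, not an expectation for this trial. The share d of AF-free subjects who leave after the Month 6 visit is 5% to 30%.

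**Step 1: leaving unrelated to later AF.** Let the conditional failure risk be equal before and after Month 6: f = 1 − √0.70 = 0.1633, so 1 − f = 0.8367.

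Available-data proportion = (1−f)²(1−d) / [1 − (1−f)d]. At d = 20% this is 0.56 / (1 − 0.1673) = 67.3%.

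| d | Available data | Bias (points) |
|---|---|---|
| 5% | 69.4% | −0.6 |
| 10% | 68.8% | −1.2 |
| 20% | 67.3% | −2.7 |
| 30% | 65.4% | −4.6 |

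For S from 77% to 55%, the bias is −1.0 to −1.5 points at d = 10% and −2.3 to −3.3 at d = 20%. Kaplan-Meier on nominal visit times gives 0.8367 × 0.8367 = 70.0%. In 6,000 simulated trials of 25 it averaged 70.0% at d = 10% and 69.9% at d = 20%.

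**Step 2: check with a different model.** Let failure and loss times be uniform over months 3 to 12, with total loss L. The proportion is 0.7(1−L) / [0.7(1−L) + 0.3(1−L/2)]. At L = 20% this is 0.56/0.83 = 67.5%; at L = 28% it is 0.504/0.762 = 66.1%. Both agree with step 1 in direction and size.

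**Step 3: leaving related to later AF** (S = 70% among stayers, d = 20%). Suppose leavers have RR times the later failure risk.

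- RR = 2: truth = 0.8367 × (0.8 × 0.8367 + 0.2 × 0.6733) = 67.3%. Available data give 67.3% (no bias); Kaplan-Meier gives 70.0% (+2.7).
- RR = 3: truth = 0.8367 × (0.8 × 0.8367 + 0.2 × 0.5101) = 64.5%. Available data are +2.7 points off and Kaplan-Meier +5.5.

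Over S = 55% to 77% and d = 10% to 20%, the available-data bias is zero at RR of about 1.8 to 2.1.

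**Step 4: the other reading of 7.4.** If AF-free leavers count as successes, the proportion is (1−f)[(1−d)(1−f) + d]. With independent leaving this is 0.8367 × 0.8530 = 71.4% at d = 10% and 0.8367 × 0.8693 = 72.7% at d = 20%, so the bias is upward.

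**Step 5: size against precision.** Take 25 subjects: 4 fail by Month 6, 3 leave AF-free, 3 of the remaining 18 fail later and 15 succeed.

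- Available data: 15/22 = 68.2% (exact 95% CI 45.1% to 86.1%).
- Nominal-visit Kaplan-Meier: 21/25 × 15/18 = 70.0% (51.2% to 88.8%).
- Bounds: 15/25 = 60% if all leavers fail, 18/25 = 72% if none do.

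**Step 6: why actual visit dates would be wrong.** Suppose nobody drops out and Month 12 visits are spread uniformly over days 335 to 395. Failures found after day 365 are then missed by a curve read at day 365, which gives 0.8367 × exp(−0.1633 × ln 2) = 74.7% against a true 70%. The simulated average was 74.8%, and 74.0% at d = 10%. Read at day 395, the curve averaged about 45% with a standard deviation of about 25 points, because hardly anyone is still at risk.

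**The case against.** A reader might infer three stronger things, and the documents support none of them.

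*That 7.4 orders AF-free leavers out of the denominator.* It does not say so. It bars imputation and restricts analysis to available data, and 5.11 does not settle the matter. Removal is the natural reading, but counting such subjects as event-free is not excluded and would reverse the bias (step 4). What is certain is that the denominator is undefined.

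*That the success rate is biased downward, whatever the pattern of loss.* This holds only if leaving is unrelated to later AF. The documents give no dropout rate or mechanism, and step 3 shows the bias vanishing and then reversing.

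*That Kaplan-Meier removes the bias at no cost.* It needs independent censoring, and when leavers do worse it can be further from the truth than the crude proportion. Rhythm is sampled mainly at two visits with wide windows. The visit lists in 5.13.5 to 5.13.7 do not ask for AF onset dates. On actual visit dates the method adds an error larger than the one it corrects at 10% or 20% leaving (step 6). A curve that starts at the end of blanking has no place for failures by repeat ablation during blanking. Censoring AF-free deaths estimates success as if nobody died.

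The materiality objection is also fair: this is a descriptive additional observation, one subject in 25 is 4 points, and the interval for 18/25 spans 50.6% to 87.9%. These objections limit the size of the point and shape the remedy. They leave the asymmetry in place, and unlike sampling error it would not shrink if the rule were carried into a larger study.

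**Conclusion.** The point stands as a cheap improvement. Sections 5.4.5 and 7.4 leave the denominator open. On their natural reading, early failures are kept and AF-free leavers, including AF-free deaths, are dropped. With an assumed true success of 70% and leaving unrelated to later AF, the proportion is about 1 to 3 points low at 10% to 20% loss. The direction is conditional: no bias at about twice the later failure risk in leavers, upward beyond that, and upward if AF-free leavers are scored as successes. The success rate, loss rate, relative risk and spread of visit dates are all assumptions. The primary and secondary endpoints are outside this point.

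**What to change.** In 5.4.5 and 7.4:

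1. Define the denominator for 12-month therapeutic success.
2. Report the numbers of failures, confirmed successes and subjects of unknown status, with the proportions that result if all unknowns fail and if all succeed.
3. Add a Kaplan-Meier estimate on nominal visit times, or an interval-censored estimate, with a 95% CI. Censor AF-free withdrawn or lost subjects at their last rhythm assessment.
4. Count repeat ablations during blanking as failures at time zero so that they stay in the estimate.
5. State how AF-free deaths are handled in each summary.

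Two sets of passages affect the scoring and must be reconciled. The Month 12 visit text in 5.13.7 gives a 6-month (180±30 day) timing, against 365±30 in Table 4. Section 5.13.5 allows gaps found at the 3-month remapping to be closed by ablation, while 5.4.5 counts any repeat ablation through Month 12 as failure.

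The cost is a short paragraph of analysis text, with no new assessments. The added estimate relies on independent censoring, which 25 subjects cannot verify, so the counts and bounds should always appear beside it.
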